9 STATISTICAL METHODS

9.1 Statistical and Analytical Plans

This section presents a summary of the planned statistical analyses. A detailed plan describing the analyses to be conducted will be defined prior to database lock and will include the determination of rules for major and minor protocol deviations. Any deviation from the analysis specified in the protocol or the statistical analysis plan will be detailed and justified in the clinical study report.

9.2 Populations to be Analyzed

Allocation of patients to the analysis populations (and whether any patients or specific data from a patient will be excluded) will be determined at the pre-database lock meeting.

The full analysis set (FAS) will consist of all randomized patients with sufficient data collected after intake of study treatment to compute the pharmacodynamic parameters based on FEV₁ on at least one occasion.

The per-protocol set (PPS) will consist of all patients in FAS without any major protocol deviations considered to influence the treatment effect of RPL554.

The safety set will consist of all randomized patients who took at least one dose of study medication.

The PK data set will consist of all randomized patients with blood sampling performed and a quantitative value of tiotropium and/or RPL554 concentration determined.

9.3 Study Endpoints

9.3.1 Primary Endpoint

The primary endpoint is the change from baseline in peak FEV₁ (maximum value during 3 hours following dose) at Visit 6 (after 4 weeks of treatment).

9.3.2 Secondary Endpoints

- Change from baseline in average AUC_{0-3h} FEV₁ at Visits 2 to 6
- Change from baseline in average AUC_{0-12h} FEV₁ at Visits 2 and 6
- Change from baseline in peak FEV₁ at Visits 2 to 5
- Change from baseline in morning trough FEV₁ at Visits 3 to 6
- Change from baseline (i.e., mean over the last 7 days of Run-in) to the mean weekly values over weeks 1 to 4 in COPD symptoms, as measured by daily e-diary (E-RSTM:COPD)
- Change from baseline in the SGRQ-C questionnaire at Visits 4 and 6
- TDI questionnaire at Visits 4 and 6
- PGAC questionnaire at Visits 4 and 6
- Change from baseline (i.e., mean over the last 7 days of Run-in) to the mean weekly values over weeks 1 to 4 in rescue medication use
- Change from baseline in peak and average AUC_{0-3h} FVC at Visits 2 to 6, in average AUC_{0-12h} FVC at Visits 2 and 6 and in morning trough FVC at Visits 3 to 6.

- Trough plasma concentration of tiotropium at Visits 2 and 4, and trough plasma concentration of RPL554 at Visit 4
- Safety and tolerability:
 - Continuous monitoring of adverse events
 - Laboratory safety tests (hematology, blood chemistry and urinalysis)
 - 12-lead ECG (including QTcF and heart rate), supine vital signs (blood pressure and pulse rate)

9.3.3 *Exploratory Endpoints*

- Change in peak and average AUC_{0-12h} FEV₁ between Visits 2 and 6
- Change from baseline in IC after 4 weeks of treatment
- Change from baseline in the CAT questionnaire at Visits 4 and 6
- Change from baseline (i.e., mean over the last 7 days of Run-in) to the mean weekly values over weeks 1 to 4 in morning symptoms
- Change from baseline (i.e., mean over the last 7 days of Run-in) to the mean weekly values over weeks 1 to 4 in morning activity limitation

9.4 Statistical Methods

In general, unless stated otherwise, continuous variables will be summarized using descriptive statistics (number of patients, mean, standard deviation, median, minimum and maximum values) and for categorical (nominal) variables, the number and percentage of patients will be used.

All hypothesis testing will be done using two-sided alternative hypotheses. P-values less than 5% will be considered statistically significant.

9.4.1 *Patient Disposition*

The number of patients enrolled, randomized, completed or withdrawn (with reason for withdrawal) will be summarized.

9.4.2 *Protocol Deviations*

All protocol deviations collected will be divided into critical, major or minor categories. Prior to database lock protocol deviations will be reviewed and consequences for inclusion of patients in various analysis population sets determined and documented.

9.4.3 *Demographics and Other Baseline Characteristics*

Demographics and baseline characteristics (including pre- and post-bronchodilator FEV₁ [both in liters and in percentage of predicted normal], post-bronchodilator FEV₁/FVC, FEV₁ reversibility, duration of COPD [time since diagnosis], smoking habits including number of pack years, number of patients taking prior COPD medications by therapeutic class including ICS, LABA, LAMA or combinations thereof) will be listed and summarized appropriately.

Medical history, prior and concomitant medications, viral serology results, mMRC score, pregnancy test and/or FSH test results from females and chest X-ray findings will be listed.

9.4.4 *Extent of Exposure and Treatment Compliance*

Compliance will be calculated based on two parameters – the number of used and unused vials returned and the dosing recorded in the e-diary. Total exposure will be based on the compliance with dose and the dose group the subject was randomized into. For in-clinic dosing, the RPL554 exposure will be calculated based on the nominal dose.

9.4.5 *Efficacy/Pharmacodynamics*

The FAS will be the primary efficacy population; outcomes based on the PPS will be considered as a sensitivity analysis.

FEV₁ and FVC will be summarized as actual value and change from baseline using descriptive statistics over time for all treatments and both study parts.

The peak effect on FEV₁ will be computed as the maximum value in the 3 hours after dosing. The average effect will be calculated as the AUC divided by the length of the time interval of interest. For analysis, the peak, average and trough FEV₁ will be included as the change from the pre-dose Day 1 baseline value.

Computed pharmacodynamic parameters based on FEV₁ will be compared between the treatments using a mixed model for repeated measures (MMRM) with fixed effects for treatment, visit and treatment by visit interaction, baseline as covariate, patient as random and covariance structure by visit.

RPL554 treatments will be compared to placebo using a closed testing procedure. The highest dose (3 mg) will first be compared to placebo, and if found statistically significant then the next dose (1.5 mg) will be compared to placebo, and so on. Secondarily, doses will be compared pairwise. Results of the comparisons will be expressed as the mean effect difference with 95% confidence intervals and associated, 2-sided, p-value.

Pharmacodynamic parameters based on FVC, average daily use of rescue medication, average weekly E-RS™:COPD means, SGRQ-C, TDI, CAT and PGAC scores will be compared between the treatments using similar MMRM models as for the primary variable. Subdomain scores of the E-RS™:COPD, SGRQ-C and weekly morning symptoms and activity limitation will be summarized and subjected to exploratory analyses.

The number of COPD exacerbations will be summarized by treatment group.

As a sensitivity analysis the primary endpoint (peak FEV₁ at Visit 6), the average AUC_{0-12h} FEV₁ at Visit 6 and the total E-RS™:COPD score at week 4 will also be compared using analysis of covariance (ANCOVA) models with fixed factors for treatment, reversibility strata and the pre-dose baseline value as a covariate.

9.4.6 *Pharmacokinetics*

Plasma concentrations of tiotropium and RPL554 will be summarized by dose level using descriptive statistics (n, geometric mean, coefficient of variation, arithmetic mean, standard deviation, minimum, maximum and median).

9.4.7 *Safety*

Safety data including laboratory safety tests, 12-lead ECG, vital signs and physical examinations, will be summarized by treatment group and time point of collection, when appropriate, for each of the two parts separately. For continuous variables, the change from baseline (pre-dose at Visit 2) to each post-dose time point will also be calculated and summarized. Data will further be illustrated by shift tables (showing changes from low/normal/high) and shift plots for selected time points. Separate listings will be generated of abnormal values occurring after the first dose of study treatment.

Coded adverse event terms will be presented by system organ class (SOC) and preferred term and summarized by treatment group for each part. Summary tables by treatment group with total number and number of patients with adverse events, SAEs, adverse events leading to discontinuation of study treatment, causally related adverse events and severe adverse events will be produced. Further SAEs, causally related adverse events and adverse events of each intensity will be summarized by SOC and preferred term.

9.4.8 *Handling of Withdrawals or Missing Data*

Imputation of data for calculation of average (AUC) effects for FEV₁ and FVC will be described in the statistical analysis plan. No other imputation of missing data will be performed for the parameter computations. For the sensitivity ANCOVA analyses, missing data will be imputed using the last observation carried forward method prior to analysis.

All available data from all dosed patients who have received study treatment will be listed and summarized. Any unscheduled or unplanned readings will be presented within the patient listings, but only the scheduled readings will be used in any summaries.

9.4.9 *Interim Analyses*

No formal, unblinded interim analysis is planned for the study. To assess the plausibility of the assumptions in the sample size calculation, an estimate of the standard deviation of peak and AUC_{0-3h} FEV₁ will be made based on blinded data after completion of 125 patients. If the estimated standard deviations are markedly higher than the 200 mL assumed (>20%), a revised sample size estimation using the new standard and the previously used detectable difference (89) will be made. If the outcome is an increase of the sample size, an amendment will be submitted for approval.

9.5 *Determination of Sample Size*

The standard deviation for peak FEV₁ is estimated to be 200 mL. With a 2-sided test at a 5% significance level and 73 evaluable patients per group, there will be 80% power to detect a true difference of 93 mL between any two treatments. This detectable limit has been considered sufficient to identify an effective dose of RPL554. Assuming a 10% early withdrawal rate, 80 patients per group will be randomized.

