Main Criteria for Eligibility:	Male and female patients 40 to 80 years old with moderate to severe COPD, with a post-bronchodilator FEV ₁ of 30 to 70% of predicted and FEV ₁ /FVC ratio of ≤ 0.70 . Patients must have a minimum score of 2 on the modified Medical Research Council (mMRC) dyspnea scale. They must have at least a 10 pack-year smoking history, and may be a former smoker or current smoker. At randomization, patients must continue to have a minimum score of 2 on the mMRC, demonstrate pre-dose FEV ₁ of 30 to 70% of predicted and be compliant with e-diary and tiotropium use during the 14 days between Visits 1 and 2. Patients must be clinically stable without recent COPD exacerbations or hospitalizations. They must not have uncontrolled disease or chronic heart failure.
Study Treatments:	Patients will be randomized to one of the following treatment arms: 
RPL554 0.375 mg twice dailyRPL554 0.75 mg twice dailyRPL554 1.5 mg twice dailyRPL554 3.0 mg twice dailyPlacebo twice daily All eligible patients will take open-label tiotropium provided by the study centers during the run-in and treatment periods.
Duration of Treatment:	The approximate planned duration for each completed patient will be 14 days of run-in and 28 days of treatment with study medication.
Statistical Methods:	Treatments will be compared using mixed model for repeated measures (MMRM) adjusting for treatment, visit and treatment by visit interaction. Each RPL554 nebulized formulation treatment will first be compared to placebo using a closed test procedure starting with the highest dose of RPL554. With an FEV ₁ standard deviation estimated at 200 mL, a 2-sided test at a 5% significance and 73 evaluable patients per group, there will be an 80% power to detect a true difference of 93 mL between treatments. Assuming approximately a 10% early withdrawal rate, 80 patients per group are planned to be randomized.

TABLE OF CONTENTS AND LIST OF TABLES AND FIGURES

Table of Contents

SPONSOR SIGNATURE PAGE	2
INVESTIGATOR SIGNATURE PAGE	3
CONFIDENTIALITY STATEMENT	3
CONTACT LIST	4
DETAIL OF AMENDMENTS SINCE THE PREVIOUS VERSION	5
SYNOPSIS	6
TABLE OF CONTENTS AND LIST OF TABLES AND FIGURES	9
Table of Contents	9
List of Tables and Figures	13
LIST OF ABBREVIATIONS	14
1 INTRODUCTION	16
1.1 Disease and Study Medication Review	16
1.2 Summary of Risks and Benefits	18
2 OBJECTIVES	19
2.1 Primary Objective	19
2.2 Secondary Objectives	19
2.3 Exploratory Objectives	19

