4.2. Interim Analysis

There will be no formal, unblinded interim analysis for this study. To assess the plausibility of the assumptions in the sample size calculation, peak FEV₁, trough FEV₁, AUC₀₋₃ FEV₁ and AUC_{0-12h} FEV₁ will be calculated on blinded data after completion of 125 patients. If the estimated standard deviation has an increase of 12% or less, then there will be no revised sample size made. However, if the estimated standard deviation has an increase of 20% or more, a revised sample size estimation using the new standard deviation and the previously assumed difference of 93 mL will be performed. If the increase in estimated standard deviation will be between 12% and 20% then a decision to review the sample size will be taken based on further examination of the data.

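### Protocol 9.4.9 re-estimates the sample size with a difference of 89 instead of the 93 mL used everywhere else, and the SAP triggers the re-estimation by a different rule

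*Protocol*

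**What the plan says.** Both documents plan a blinded check of the SD after 125 patients, against the 200 mL assumed in the design.

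**Difference to be detected**
- Protocol 9.4.9 re-estimates "using the new standard and the previously used detectable difference (89) will be made". No unit is given.
- Protocol 9.5: with 73 evaluable patients per group, "there will be 80% power to detect a true difference of 93 mL between any two treatments". The synopsis agrees: "there will be an 80% power to detect a true difference of 93 mL between treatments".
- SAP 4.2 re-estimates "using the new standard deviation and the previously assumed difference of 93 mL will be performed". SAP 16.6 also fixes the difference at 93 mL in the two calculations that take it as known.

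**Trigger**
- Protocol 9.4.9 acts only when the SD is more than 20% above 200 mL.
- SAP 4.2 has three zones. At an increase of 12% or less there is no revision. It revises "if the estimated standard deviation has an increase of 20% or more". Between the two it leaves the matter to a decision after a further look at the data.

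**Safeguard and declaration**
- Protocol 9.4.9: "If the outcome is an increase of the sample size, an amendment will be submitted for approval".
- SAP 3.3 declares no departure from the analyses in the protocol.

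**The concern.** Protocol 9.4.9 presents 89 as the figure already in use, so it reads as a cross-reference and not as a new target. The figure it should point to is 93 mL. A re-estimation run from the protocol would therefore start from an input that the design never used, and would give a larger trial than one run from the SAP.

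The two trigger rules can also disagree on whether to re-estimate at all. The SAP allows a judgement between 12% and 20% that the protocol does not mention, and it does not list this as a change. SAP v1.0 is dated 05DEC2019, after the planned study period of May to November 2019. The re-estimation may therefore already have been run. If so, what matters is the record of which difference and which threshold were applied.

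**Working it through.** **Inputs.** Two-sided 5%, 80% power, SD 200 mL, 73 evaluable per group, 10% withdrawal and 80 randomized per group (Protocol 9.5); five equal arms (Protocol 3.1); two-sample t-test (SAP 16.6). SDs above 200 mL other than the thresholds are illustrative.

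**1. Reproduce the design.** By the normal approximation, n per arm = 2 × (1.960 + 0.842)² × (SD/difference)².
- At 93 mL: 2 × 7.849 × (200/93)² = 72.6, so 73. This is the protocol's figure.
- The t-test (noncentral t) gives 73.57. With n = 73 its power is 79.7% and the detectable difference is 93.4 mL. The stated design holds.

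**2. Try 89 mL in the same design.**
- Normal: 2 × 7.849 × (200/89)² = 79.3, so 80. The t-test gives 80.24, so 81.
- With n = 73 the t-test power at 89 mL is 76.1%.
- With n = 80 the detectable difference is 89.1 mL. So 89 fits the number to be randomized, not the number evaluable. That is a plausible origin, but only an inference.

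**3. Effect on a re-estimated size.** At any SD, 89 mL needs (93/89)² = 1.092 times as many patients as 93 mL. t-test, 80% power, rounded up; randomized = evaluable/0.9, rounded up:

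| SD (mL) | Evaluable per arm, 89 / 93 mL | Randomized per arm, 89 / 93 mL | Extra randomized, five arms |
|---|---|---|---|
| 241 | 117 / 107 | 130 / 119 | 55 |
| 250 | 125 / 115 | 139 / 128 | 55 |
| 260 | 135 / 124 | 150 / 138 | 60 |

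The extra evaluable patients over five arms are 50, 50 and 55. At SD 241 mL, 117 per arm has 83.6% power for 93 mL, against 80.2% with 107.

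**4. Compare the triggers.** The thresholds are 200 × 1.12 = 224 mL and 200 × 1.20 = 240 mL.

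| Blinded SD | Protocol 9.4.9 | SAP 4.2 | Power for 93 mL at 73 per arm |
|---|---|---|---|
| 224 mL (12%) | no re-estimation provided for | no revision | 70.2% |
| 230 mL (15%) | no re-estimation provided for | discretionary; 97 per arm if revised to 80% power | 68.0% |
| 240 mL (20%) | no re-estimation provided for | revision; 106 per arm | 64.3% |
| above 240 mL | re-estimate with 89 | re-estimate with 93 mL | below 64.3% |

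**5. Related difference.** Protocol 9.4.9 estimates the SD for peak and AUC0-3h FEV1. SAP 4.2 and 16.6 add trough and AUC0-12h, and SAP 16.6 fits two models for peak. Neither document says which estimate governs the trigger if they disagree.

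**The case against.** The SAP is the detailed plan that Protocol 9.1 foresees, and it uses 93 mL consistently, as do the synopsis and Protocol 9.5. A statistician working from the SAP would not use 89. The check is blinded, any increase needs an approved amendment in which the difference would have to be stated, and neither the primary analysis nor the testing order changes. All of this is right, and it limits the weight of the point. It does not make the protocol text correct: the increase runs through a protocol amendment, and the protocol paragraph that governs it carries the wrong input.

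On the trigger, Protocol Section 9 describes itself as a summary and does not forbid a review below 20%, so the SAP's middle zone could be read as elaboration. The contrast at exactly 20% is an edge case with little practical weight. SAP 3.3 speaks of the analysis, which may not cover a sample-size check. The SAP cites protocol version 5.0, and the protocol text available for review does not show its version. These are fair readings. Even so, a decision zone that depends on the data and is absent from the protocol should be declared somewhere.

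The exact counts depend on convention. The normal approximation gives 116 and 106 at SD 241 mL. Dividing by 0.9 does not reproduce the protocol's step from 73 to 80, since 73/0.9 = 81.1. The gap of about 10 evaluable patients per arm remains either way.

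**Conclusion.** The concern holds and should be corrected. The 89 in Protocol 9.4.9 conflicts with every other statement of the design difference and does not fit 73 evaluable patients per group. Followed literally, it would raise a re-estimated size by about 9%, or 10 to 11 evaluable patients per arm for SDs from 241 to 260 mL. Separately, the two documents differ on whether to re-estimate between 12% and 20%, and at exactly 20%.

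The effect is conditional. The 89-versus-93 conflict matters only if a re-estimation is run, and the trigger conflict only if the blinded SD is more than 12% above 200 mL. The figures assume a two-sample t-test, 80% power and a two-sided 5% level. Whether the re-estimation has already taken place is inferred from dates, not stated.

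**What to change.** - Protocol 9.4.9: replace 89 with 93 mL, with the unit.
- Use one trigger rule in both documents, including whether exactly 20% counts, or list the 12% and 20% rule of SAP 4.2 as a change in SAP 3.3. The same edit can name the endpoint and model whose SD governs.
- If the re-estimation has already been run, state in the study report which difference and threshold were used and what was decided.

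The cost is wording only. At a given SD, the corrected figure gives a re-estimated trial about 10 evaluable patients per arm smaller than the current protocol text would.

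Optional, and not an error: Protocol 9.5 could add that 80% is the power of a single pairwise comparison, and that lower-dose tests against placebo in the gated sequence have less, by an amount that depends on the dose-response.

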10 ETHICAL CONSIDERATIONS

10.1 Guidelines

The study will be performed in accordance with ICH GCP guidelines, the principles outlined in the Declaration of Helsinki (1996), the protocol and applicable regulatory requirements.

10.2 Institutional Review Board and Regulatory Approval

The Sponsor will supply all background data necessary to enable submission to the appropriate institutional review boards and regulatory authorities. The study will not commence before formal ethical and regulatory approvals have been granted.

All changes or revisions of this protocol will be documented. The reason for the amendment will be stated. The Sponsor will ensure ethical and regulatory approval is obtained for all substantial amendments to the original approved documents.

10.3 Informed Consent Process

It is the responsibility of the Investigator to obtain written informed consent from patients. All consent documentation must be in accordance with applicable regulations and ICH GCP. Each patient is requested to sign and date the informed consent form after (s)he has received and read the patient information sheet and received an explanation of what the study involves, including but not limited to: the objectives, potential benefits and risk, inconveniences and the patient's rights and responsibilities. Patients will be given adequate time to evaluate the information given to them before signing the informed consent form.

One original of the signed informed consent form must remain on file and must be available for verification by the study monitor at any time. A second original of the informed consent form plus the patient information sheet must be given to the patient or the patient's legally authorized representative.

10.4 Patient Confidentiality

Data collected during this study may be used to support the development, registration or marketing of the study medication. The Sponsor will control all data collected during the study and will abide by the European Union Directive on Data Privacy concerning the processing and use of patient's personal data. For the purpose of data privacy legislation, the Sponsor will be the data controller.

After patients have consented to take part in the study, their medical records and the data collected during the study will be reviewed by the Sponsor and/or its representatives. These records and data may, in addition, be reviewed by the following: independent auditors who validate the data on behalf of the Sponsor; regulatory authorities and the institutional review board which gave its approval for this study to proceed.

Although patients will be known by a unique number, their initials will also be collected and used to assist the Investigator to reconcile data clarification forms, for example, that the results of study assessments are assigned to the correct patient. The results of this study containing the unique number, but not the patient's initials and relevant medical information may be recorded and transferred to and used in other countries throughout the world, which may not afford the same

level of protection that applies within the European Union. The purpose of any such transfer would be to support regulatory submissions made by the Sponsor in such countries.

